6.3.3. Objective measures of health

In addition to using occurrence of symptoms as an objective measure of health, we will use the large-scale sample survey to collect anthropometric information on all household members under age 60 months. This will allow us to measure:

• % of children with low height for their age (stunting)

• % of children with low weight for their height (wasting)

We will also collect measures of self-reported ability to perform Activities of Daily Living (ADLs) (e.g., ability to walk one mile) which will allow us to construct

• % of individuals that perform basic ADLs with difficulty

The large-scale sample survey and the logbook will collect data for the following indicators for all health incidents (relying on four-week recall in surveys) and for major health incidents, as previously defined (relying on 12-month recall in surveys):

•% of individuals seeking any treatment for a given health incident

• % of individuals visiting a public health facility first or at all for treatment for a given health incident

• % of individuals getting treatment by other means (traditional, private, self care, etc.) for a given health incident

• Average number of days before seeking treatment for a given health incident

• % of households obtaining trained medical advice before drug purchase

In addition, data for the following indicators will be collected relying on 12-month recall:

• % of individuals forgoing treatment for a major health incident (due to high expense)

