6.1. Statistical Methods

To estimate the causal effect of health insurance on household health and economic outcomes, we will implement a number of estimators. The overall econometric technique is to generate multiple estimates of the effect of insurance on the outcomes of interest, thus allowing us to construct a credible range of the estimated program effect. To begin with, we will construct a lower bound for the program effect the Intention-to-Treat effect. Here, outcomes at baseline will be differentiated from outcomes in the follow-up, across large and small coupon winners. This estimate provides a credible lower bound for the true program effect, because many of the large coupon winners will not take up insurance, while some of the small coupon winners will, yielding an underestimate of the true program effect. Formally, we will run a regression that includes a vector of individual fixed effects (individuali) to absorb characteristics of the household or individual, observed or unobserved, that do not change over time and a vector of year fixed effects (year t) to control for changes over time that affect all individuals (or households). We can also control for

This section outlines our methodology for achieving each goal. For objectives 1 through 3, we include a list of indicators that we plan to measure using our survey instruments. Note that the final list of indicators will depend on pre-test results, and on the power we have to measure SKY impacts using each indicator with the given study design.

Methodology for Objective 1: The Causal Effect of Health Insurance

J and I time-variant individual- and household-level covariates (Xjt and Zjit) that might affect health, health care utilization, and other outcomes, e.g., current household income. Thus, we can estimate:

Yjivt = β postit * large-couponi + γ postit + Σ li=1 α Xit + Σ Jj=1 δ Zjit + individualj+ yeart + Uvt + ϵ jivt

In this specification, postit indicates follow-up observations, Uvt represents village-level shocks collected in the village leader survey, and ɛjivt is a random error term representing individual variation from the mean. The coefficient β is the difference-in-differences estimate of the effect of being offered a high-value coupon. Outcome indicators (the Yjivt in the equation above) for Objective 1 are listed below.

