To measure selection into insurance, we will run five sets of analyses. First, we will look at average baseline characteristics of households that buy SKY and compare them to those who don't buy SKY. We will also run a logistical regression to determine the impact of each indicator on the purchase of insurance (where decision to purchase (0 or 1) is on the left- hand side and household and health facility quality characteristics are on the right-hand side of the equation).

Second, we will compare characteristics and average health care utilization of households that buy SKY at different prices, to examine whether a lower price induces more risk pooling (that is, attracts a healthier applicant pool).

Third, we will use external sources of data—the Cambodia Demographic Health Survey (DHS) and 2008 Census —to compare the profiles of village members who attend SKY village meetings and of SKY members to the general population (at the national, provincial and possibly district level). In the household survey our demographic measures (household size and members' age and sex) and some of our health (e.g., body mass index, that is, weight for height) and socioeconomic status (e.g., education) data are directly comparable to the DHS.

Fourth, we will examine selection using SKY data on membership and member utilization of health facilities. To

illustrate the possibilities, in 2007 all but one of the SKY members who had used a health center at least once renewed their membership, which was a far higher renewal rate than among those who had not used a facility at least once. This is a simple analysis using incomplete data, but illustrates the potential for such data to provide important insights into who is keeping and who is dropping insurance.

Finally, the Village Monograph will give us an in-depth qualitative study of how households make the decision to purchase insurance, how they use health facilities differently when covered by it, and how they decide to renew or drop insurance—all of which help us understand selection into the insurance market.

B. Predictors of Take-up

We will use the following measures that are collected using the household survey (described above) to predict take-up of SKY insurance:

• Wealth/income indicators (e.g., a wealth index created by asset ownership)

 Demographic characteristics of the household (age of members, number of members, gender and age of head/primary decision-maker, etc.)

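### Child height and weight, the only physically measured health outcomes, are listed solely as % stunted and % wasted; mean z-scores should be listed as the effect outcomes with the percentages alongside

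*Protocol*

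**What the plan says.** Section 6.3.3 of the protocol plans to "collect anthropometric information on all household members under age 60 months". It derives two indicators from these data: the percentage "of children with low height for their age (stunting" and the percentage "of children with low weight for their height (wasting". It states no cut-off and lists no mean or other continuous form.

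The other items in the section are not physical measurements. One is the occurrence of symptoms, gathered in the survey ("In addition to using occurrence of symptoms as an objective measure of health"). The other is "measures of self-reported ability to perform Activities of Daily Living (ADLs".

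Weight relative to height appears once more, under the methodology for Objective 2, as "health (e.g., body mass index, that is, weight for height". There it serves to compare meeting attenders and members with an external survey, not to estimate an effect of insurance.

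Two statements in section 6.1 also bear on the point. On the indicators, "the final list of indicators will depend on pre-test results, and on the power we have to measure SKY impacts using each indicator". On the analysis, "The coefficient β is the difference-in-differences estimate of the effect of being offered a high-value coupon", in a model with individual fixed effects. The Statistical Appendix adds an instrumental-variables estimate based on the coupon.

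**The concern.** Objective 1 includes objective health measures among its outcomes. Within section 6.3.3 only the anthropometry is physically measured, so a finding on measured health rests on these two indicators. A cut-off records whether a child lies below a line and ignores how far above or below. If insurance moves the whole distribution slightly, the percentage needs more children than the mean to show it.

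The signal is diluted in either form. Table 2 assumes that 40% of large-coupon and 6% of small-coupon households buy, a difference of 34 percentage points. In the coupon comparison, an effect in households induced to insure therefore appears at about a third of its size. A further avoidable loss makes an uninformative result on measured health more likely than the data require.

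**Working it through.** The protocol has no figure to reproduce here. It gives no prevalence, standard deviation, effect size, power or number of children for anthropometry. The prevalences, effect size, error rates and correlations below are assumptions.

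**1. Cross-sectional loss.** Let the score be normal with SD 1, let p be the share below the cut-off, and let z = Φ⁻¹(p). For a small uniform shift, the efficiency of the percentage relative to the mean is

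E = φ(z)² / [p(1 − p)], and the loss is 1 − E.

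At p = 0.50: φ(0) = 0.3989, so E = 0.1592 / 0.25 = 0.637. This is the maximum, so the loss is at least 36% at any prevalence.

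| Assumed p | E | Loss |
|---|---|---|
| 0.50 | 0.637 | 36% |
| 0.40 | 0.622 | 38% |
| 0.30 | 0.576 | 42% |
| 0.15 | 0.426 | 57% |
| 0.10 | 0.342 | 66% |
| 0.08 | 0.300 | 70% |
| 0.05 | 0.224 | 78% |

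This gives 36-42% for stunting at 30-50% and 57-78% for wasting at 5-15%.

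**2. Check at a finite shift.** Assume a 0.1 SD difference between coupon groups, two-sided alpha 0.05, 80% power and no clustering. The mean score needs 1,570 children per group. With p = 0.40 falling to Φ(z − 0.1) = 0.362, the percentage needs 2,551, a loss of 1 − 1,570/2,551 = 38%. With p = 0.08 falling to 0.066, it needs 5,545, a loss of 72%. Both agree with the table.

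**3. Planned difference-in-differences.** Take children measured at two waves, with correlation ρ between scores and r between the yes/no results. The variances of the change are 2(1 − ρ) and 2p(1 − p)(1 − r), so the efficiency becomes E × (1 − ρ)/(1 − r). Under bivariate normality r is smaller than ρ, so the percentage gains less from differencing.

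- p = 0.40, ρ = 0.5, r = 0.330: 0.622 × 0.5/0.670 = 0.464, loss 54%.
- p = 0.40, ρ = 0.7, r = 0.490: 0.622 × 0.3/0.510 = 0.366, loss 63%.
- p = 0.08, ρ = 0.5, r = 0.234: 0.300 × 0.5/0.766 = 0.196, loss 80%.
- p = 0.08, ρ = 0.7, r = 0.393: 0.300 × 0.3/0.607 = 0.148, loss 85%.

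The instrumental-variables estimate divides the coupon effect by the same first-stage coefficient for either outcome, so the comparison carries over to it.

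**4. If the shift is not uniform.** Suppose only the lowest share f of children gain (f at least p), each by the same small amount d. The percentage changes as before, but the mean moves by only f × d, so the cross-sectional efficiency becomes E/f². The two forms break even at f = √E: √0.622 = 0.79 at p = 0.40 and √0.300 = 0.55 at p = 0.08. Below that share the percentage is the more sensitive form. The advantage of the mean therefore depends on an effect spread over most of the distribution.

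**The case against.** The best reply is that the protocol does not confine the analysis to percentages. Section 6.3.3 says what the measurements make it possible to measure, the measurements themselves are kept, and section 6.1 leaves the indicator list open. A later analysis could add a mean score. This stands as far as the data go: nothing collected is thrown away, and a reader who infers that the plan discards measurements goes too far. But the open list does not supply the continuous score. It makes power a criterion for the final list, and for a broad shift that criterion favours the score. Adding it only after seeing null percentages would look post hoc.

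A second reply is that insurance may work mainly through treating sick children, and so on the lower tail. This also stands. The documents do not say where in the distribution an effect would fall, and step 4 shows that the percentage can then do as well or better. It is a reason to keep both forms, not to list only the percentages.

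A third reply is that these are two indicators among many, that no sample-size claim rests on them, and that percentages are easier for policy readers. All true. This limits the weight of the point but does not remove it.

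**Conclusion.** The point holds as an improvement at no field cost; it is not a contradiction or an error of fact in the protocol. The only physically measured health outcomes are listed solely in yes/no form. For a uniform shift in a normal score this loses at least 36% of the information: about 36-42% for stunting at an assumed 30-50%, and about 57-78% for wasting at an assumed 5-15%, in a cross-sectional comparison. The planned difference-in-differences would raise the loss if scores are correlated over time; an effect confined to the lower tail would shrink it and could reverse it.

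The documents do not support several stronger readings:

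- A single figure, such as 40% for stunting or 70% for wasting, is not a property of this trial. Those values need prevalences of about 0.34 and 0.08, and the protocol gives none.
- Nothing shows that the sample of children is too small. Table 2 counts households (2,375 in each main coupon group) and the number of children under 60 months is not stated.
- Nothing in the protocol establishes how fast height-for-age responds or how many children would cross the cut-off.
- The protocol does not present the daily-living items as physical measurements; it calls them self-reported.

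**What to change.** In section 6.3.3, list mean height-for-age z-score and mean weight-for-height z-score as the anthropometric effect outcomes, to be used in the difference-in-differences model of section 6.1 and in the instrumental-variables analysis of the Statistical Appendix. Keep % stunted and % wasted reported alongside, for policy readers and in case the effect lies in the lower tail. Do this before follow-up results are seen.

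The cost is a change of indicator wording. Classifying a child as stunted or wasted already means comparing the measurement with a reference, so no extra fieldwork or data are needed.

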6.3.1. Frequency, duration and severity of health incidents

In the household survey and logbooks, to measure the impact of insurance on frequency, duration and severity of health incidents, we will collect:

• % of individuals with any illness in the last 4 weeks

• % of individuals with a major health incident in the last 12 months (defined above)

• % of individuals with a chronic illness

 Average duration of illness (measured by number of days an individual could not perform normal activities due to illness)

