• At the end of the project, a policy brief will be produced and distributed to Ministry officials, donors, and GRET, and will be posted online.

• Results will be presented at various seminars and venues:

- Once per year, we will present a paper on the evaluation at the Cambodian Socio-cultural Research Congress held at the Royal University of Phnom Penh.

- Results will be presented at academic and non-academic seminars and presentations.

Statistical Appendix

a. Instrumental Variables

We would like to estimate the effect of having health

insurance on health care utilization (or some other outcome). We might run a regression:

1) number of health center visits = $\beta_0 + \beta$ · has health insurance + controls + ϵ .

Here, β is the effect of health insurance on the outcome, number of health center visits, and ϵ is an error term representing individual variation from the average effect of health insurance on health center visits. β 0 is a constant, representing the number of health center visits when a household does not have health insurance. Contained in ϵ is any factor that we are not including on the right-hand side of the regression.

If buying health insurance were completely random (at least among people with similar observable control variables), then an Ordinary Least Squares (OLS) regression of the above equation would give us an unbiased estimate of β . In that case, owning health insurance will not be correlated with the error term, and we say that the correlation of health insurance and the error term is equal to zero, or E(health insurance * ϵ) = 0.

Unfortunately, it is likely that buying health insurance is correlated with unobserved factors such as poor health. In that case, having health insurance will be correlated with the error term, ε , which contains the effect of unobserved influences on number of health center visits. In other words, E (health insurance * ε) is not zero. Therefore, OLS regressions of (1) are biased, meaning that the estimation of β will contain the effect of other factors besides health insurance on health. Intuitively, if sick people both have many health center visits and buy health insurance more often, it will appear that insurance raises the number of health center visits even if the causal effect is zero.

We are running a lottery for coupons that reduce the price of insurance. Thus, we can run a first-stage regression:

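### Three of the five four-week curative-use indicators are percentages among reported illnesses, so the coupon arms are compared on subsets that insurance may have changed, and no curative-use measure over all members or households is listed

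*Protocol*

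**What the plan says.** The list belonging to section 6.4.1 (printed after the text of 6.3.3) has five indicators on four-week recall for all incidents. The same list is used on 12-month recall for major incidents, which are not at issue here.

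- Percentage "of individuals seeking any treatment for a given health incident"
- Percentage "of individuals visiting a public health facility first or at all for treatment for a given health incident"
- Percentage "of individuals getting treatment by other means (traditional, private, self care, etc.) for a given health incident"
- Treatment delay, given as "Average number of days before seeking treatment for a given health incident"
- Percentage "of households obtaining trained medical advice before drug purchase"

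The first three are percentages tied to an incident, the fourth is a mean in days per incident, and the fifth is per household and tied to buying drugs.

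Section 6.3.1 lists the percentage "of individuals with any illness in the last 4 weeks" among the health outcomes that insurance may affect. Objective 1 in section 2 names use of public facilities, and substitution towards them, without restricting either to people who report illness. The Statistical Appendix, part a, explains the estimator with a count: "Here, β is the effect of health insurance on the outcome, number of health center visits". Its worked table and the later regressions take the household as the unit. No indicator in section 6.4 measures curative use over all members or all households.

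**The concern.** The lottery makes the coupon arms comparable as whole groups. It does not make those who report an illness in one arm comparable with those who report one in the other. Insurance may prevent some illness, and it may lead members to notice or mention complaints that they would otherwise have passed over. A member whose illness was prevented leaves the denominator, and a member who mentions a minor complaint enters it. The instrument is argued to be valid because the coupon is random, and that argument need not hold within a subset formed after the draw.

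Two errors can follow. Real changes in use per member can leave the indicator where it was, and the indicator can move although use has not changed.

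There is also a loss of information. Section 6.1 plans individual fixed effects. If the outcome exists only for members who are ill, only those ill in more than one round (in effect at baseline and in at least one follow-up) inform the coupon effect. That is a small and selected group.

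**Working it through.** **The plan's own figure.** The appendix illustration gives 1.5 / 0.5 = 3 more visits per household. From the entries in Table 4, (2.5 − 1.03) / 0.5 = 2.94, which rounds to 3. The figure reproduces. It concerns visits over all households, whether or not anyone was ill.

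**Inputs.** Take-up is 40% with a large coupon and 6% with a small one (notes to Table 2), a difference of 0.34. The protocol gives no illness rate, treated share or number of visits per episode, so the values below are assumptions. I count one incident per ill person.

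**Identity.** Visits per member = q × s × v, where q is incidents per member, s the share of incidents treated and v the visits per treated incident. The three percentages measure s only.

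**Case 1: use changes, indicator does not.** Assume 30 incidents per 100 members, 18 treated.
- Without insurance: 18/30 = 60%, and 18 treated episodes per 100.
- Insurance prevents 5 incidents, 3 of them treated: 15/25 = 60%, and 15 per 100.
- Change in treated episodes: −3/18 = −17%. Change in indicator: 0 points.

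The same holds upwards. With s fixed at 25%, a 10% to 50% rise in q raises visits by 10% to 50% and leaves the indicator unchanged. If v goes from 1.0 to 1.5, visits rise 50% and the indicator again stays put.

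**Case 2: indicator changes, use does not.** Insured members report 3 or 6 extra complaints per 100, none treated.
- 18/33 = 54.5%, a drop of 5.5 points.
- 18/36 = 50.0%, a drop of 10 points.

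Scaled to the comparison of arms: 0.34 × 5.5 = 1.9 and 0.34 × 10 = 3.4 points. Because the indicator is a ratio, I also pooled each arm directly.
- 3 extra complaints: 18/(30 + 0.06 × 3) − 18/(30 + 0.40 × 3) = 59.6% − 57.7%, about 2.0 points.
- 6 extra complaints: 18/(30 + 0.06 × 6) − 18/(30 + 0.40 × 6) = 59.3% − 55.6%, about 3.7 points.

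The two methods agree in order of size.

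**Case 3: extra complaints partly treated.** Assume 20 incidents per 100 members, 16 treated (80%). Add 4 complaints of which 40% are treated: (16 + 1.6)/24 = 73.3%. Treated persons rise 10% while the indicator falls 6.7 points. If the added complaints were treated at the existing 80%, the indicator would not move.

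**Fixed effects.** Assume 10% to 30% of members are ill in a four-week window, independently across the three rounds. The share ill at baseline and in at least one of two follow-ups is q × [1 − (1 − q)²]. That is 0.1 × 0.19 = 1.9% to 0.3 × 0.51 = 15.3%. Persistent illness would raise this, but never above q itself. A per-member outcome with zeros uses everyone interviewed in both periods.

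**The case against.** The best defence is that section 6.4.1 asks about treatment and choice of provider when ill. For that question an unchanged 60% in Case 1 is the right answer, and the fall in illness appears in the prevalence indicator of 6.3.1. Multiplying the two roughly recovers persons treated: 30% × 60% = 18 and 25% × 60% = 15 per 100. This stands in part. It works only if ill people have about one incident each, it misses repeat visits, and the protocol does not plan it. Nor does it repair the comparison of non-equivalent subsets.

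Other measures are on offer, but none fills the gap. Spending by provider (6.2.1) moves with the price paid, which insurance alters. Logbooks (5.5) would record every visit, but they depend on field tests, and 6.4.1 gives them the same per-incident indicators. Preventive care (6.4.2) is not curative use. The utilization averages under Objective 2 compare buyers at different prices, not coupon arms.

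The list is provisional (6.1), but the stated grounds for revising it are pre-test results and power, and neither addresses this problem. The exact denominator could be left to an analysis plan. The choice to tie the measures to an incident is made in the protocol.

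Some stronger readings do not hold. A reader might infer that every four-week indicator is a percentage per illness; three of five are. A reader might take the appendix to promise visits per person and so see a contradiction. Its unit is the household and the visit count is an illustration, so the omission is a gap and not a contradiction.

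**Conclusion.** The concern holds for the three indicators of whether and where care is sought, and for treatment delay. They condition on an event after the draw that the protocol itself treats as a possible effect of insurance, and no measure of curative use over all members or households stands beside them.

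The direction in Case 1 is arithmetic. The drop in Case 2 also requires that added complaints be treated less often than existing ones, which is plausible for minor complaints but assumed. All sizes rest on assumed rates: 5 to 10 points among those insured through the coupon, and about 2 to 3 points between arms by proportional scaling. The fixed-effects point assumes that the outcome is analysed per individual and left undefined for those not ill.

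A reader might infer that the trial's main utilization result will be reversed. The documents do not support that: no headline outcome is named, several estimates are planned, and nothing in the protocol shows that reporting will differ between the arms.

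**What to change.** For the intention-to-treat and instrumental-variable analyses, add curative-use outcomes over the last four weeks for all household members (or all households), with zero for those not ill:

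- any use of a public facility;
- any use of a private or traditional provider;
- any self-treatment;
- number of visits, if the questionnaire records it.

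Keep the per-incident percentages and treatment delay as descriptive results, and say that they are not randomized comparisons.

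The three yes/no outcomes need new definitions only, because incidents and providers are already recorded by individual. The visit count may need a question added, since the list asks only whether a public facility was used first or at all. The small downside is that an all-member measure mixes need with care-seeking, so it should be read beside the illness-prevalence indicator of 6.3.1.
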